### 11.3 Documenting / Reporting of Adverse Events by Investigator

All adverse events collected per section 11 must be fully recorded in the subject's case record form.

Documentation must be supported by an entry in the subject's file. A laboratory test abnormality considered clinically relevant, e.g., causing the subject to withdraw from the study, requiring treatment or causing apparent clinical manifestations, or judged relevant by the investigator, should be reported as an adverse event. Each event should be described in detail along with start and stop dates, severity, relationship to investigational product, action taken and outcome.

Every attempt should be made to describe the adverse event in terms of a diagnosis that encompasses the component signs and symptoms. If only nonspecific signs or symptoms are present, then these should be recorded as separate diagnoses on the pages of the case report form.

All subjects who have adverse events, whether considered associated with the use of study drug or not, must be monitored to determine the outcome. The clinical course of the adverse event will be followed according to accepted standards of medical practice, even after the end of the period of observation, until a satisfactory explanation is found or the Principal Investigator considers it medically justifiable to terminate follow-up. Should the adverse event result in death, a full

pathologist's report should be supplied, if possible.

### 11.3.1 Assessment of Causal Relationship of Study Drug

The Investigator will provide an assessment of the potential causal relationship between adverse events and study medication by determining whether or not there is a reasonable possibility that the event was caused by the study medication. The relationship or association of the adverse event to the study medication will be characterized as not related, probably not related, possibly related, probably related, or related:

**Not Related:** There is not a temporal relationship to the study drug administration or the adverse event is clearly due only to the progression of the underlying disease state, intercurrent illness, concomitant medication, concurrent therapy or other known cause.

**Probably Not Related:** There is little or no chance that the study drug administration caused the adverse event; the event is most likely due to another competing cause, including intercurrent illness, progression or expression of the disease state, or a reaction to a concomitant medication or concurrent therapy appearing to explain the reported adverse event.

**Possibly Related:** The association of the adverse event with the study drug administration is unknown; however, the adverse event is not reasonably attributed to any other condition.

**Probably Related:** When a reasonable temporal relationship exists between the adverse event and the study drug administration; significant symptoms abate upon discontinuation of the study drug and there is a reasonable explanation based on known characteristics of the study drug and there is no clear association with preexisting disease or therapy, intercurrent illness, concurrent therapy or other factor(s).

**Related:** When the adverse event is a known side effect of the study drug or there is a temporal relationship to the administration of the study drug; or the adverse event reappears upon re-administration of the study drug (rechallenge); or the significant symptoms of the adverse event abate upon discontinuation of the study drug (dechallenge).

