#### 12.6 Enhanced AE Safety Monitoring

When accrual is greater than 10 subjects, if at any time, 5 of the initial 10 treated subjects or 50% or more of all treated subjects have experienced a non-hematologic grade  $\geq$  3,4, 5 adverse event considered at least possibly related to treatment (possible, probable, or

definite), accrual will be temporarily suspended to this study for a review by the PI and the Data Integrity and Safety Committee. Grade 4 and 5 adverse events deemed “unrelated” or “unlikely to be related” will be reviewed and monitored, to assess for the emergence of a previously unrecognized treatment-related adverse event.

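### Timing alone, or a known effect alone, satisfies the top causality category, so one event can be both 'Related' and 'Probably Not Related' and fall on either side of the Section 12.6 suspension count

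*Combined protocol and SAP*

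**What the plan says.** Section 11.3.1 asks the investigator to judge causality by "determining whether or not there is a reasonable possibility that the event was caused by the study medication", then sets out five categories:

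- *Not Related*: the wording is "There is not a temporal relationship to the study drug administration or the adverse event is clearly due only to the progression", with the underlying disease and other known causes then listed.
- *Probably Not Related*: "the event is most likely due to another competing cause". Timing is not mentioned.
- *Possibly Related*: the association is unknown; "however, the adverse event is not reasonably attributed to any other condition".
- *Probably Related*: reasonable timing, abatement on stopping, an explanation from the drug's known characteristics, and no clear association with another factor, all together.
- *Related*: "a known side effect of the study drug or there is a temporal relationship to the administration of the study drug", or positive rechallenge, or positive dechallenge. Any one is enough.

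Two later sections use these judgements. Section 12.6 suspends accrual for review when "5 of the initial 10 treated subjects or 50% or more of all treated subjects" have had a non-hematologic event of grade 3 or higher, the test being an "adverse event considered at least possibly related to treatment". Section 12.5 summarises adverse events by causality.

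**The concern.** A causality scale should become harder to satisfy as it rises. Here the top level is the easiest to enter: one criterion suffices and no alternative cause need be ruled out, while the two levels beneath it require that other causes be excluded. An event with a competing explanation can therefore fail *Possibly* and *Probably* yet satisfy *Related*, and satisfy *Probably Not Related* as well.

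Such events are to be expected in this population. Section 4.2 admits patients with treated biliary obstruction, and Section 7.3.2 itself names stent migration as a cause unconnected with the study. Nausea, vomiting, diarrhea and fatigue are listed in Section 1.4.2 among the drug's common reactions, so an episode caused by the tumour still meets the known-effect criterion. External sites also score events (Sections 4.2 and 15.9), so local reading habits can differ.

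At stake are the Section 12.6 count and the Section 12.5 causality table. Either could change with the definition an investigator applies, without any change in toxicity.

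**Working it through.** **Step 1: place one event on the scale.** Take an event whose only link to the drug is timing (not a known effect, no rechallenge or dechallenge information) and vary the alternative cause.

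| Alternative cause | Definitions met | Counted by 12.6? |
|---|---|---|
| None reasonable | *Possibly Related*, *Related* | Yes under both |
| Another cause more likely | *Probably Not Related*, *Related* | No / Yes |
| Another cause is clearly the only one | *Not Related*, *Related* | No / Yes |

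The last two rows straddle the cut. Replacing timing with known effect gives the same straddle, because either criterion alone satisfies *Related*.

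**Step 2: look for a rule that resolves the overlap.** Section 11.3.1 has none. Section 11.3.3 does give a worst-case hierarchy when several actions were taken with the study drug, but nothing equivalent exists for causality.

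**Step 3: check the labels.** Section 12.6 refers to possible, probable and definite, and to unrelated and unlikely; Section 11.2 also uses definitely. The middle labels correspond to levels in 11.3.1. The end labels (definite, unrelated, unlikely) do not appear there, although they map in order to *Related*, *Not Related* and *Probably Not Related*.

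**Step 4: sensitivity of the trigger.** The plan gives no operating characteristics for 12.6, so there is no figure to reproduce. For the first limb of the rule, with per-subject probability p of a counted event and subjects independent,

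P(X ≥ 5) = Σ (k = 5 to 10) C(10,k) p^k (1−p)^(10−k).

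- p = 0.30: 0.1029 + 0.0368 + 0.0090 + 0.0014 + 0.0001 + 0.0000 = 0.150
- p = 0.40: 0.2007 + 0.1115 + 0.0425 + 0.0106 + 0.0016 + 0.0001 = 0.367

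The same formula gives 0.033 at p = 0.20 and 0.623 at p = 0.50. Suppose 10% of subjects have a dual-fit event and no other qualifying event. The probability when those subjects are not counted, and when they are, is then:

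| Base rate | Dual-fit not counted | Dual-fit counted |
|---|---|---|
| 20% | 0.033 | 0.150 |
| 30% | 0.150 | 0.367 |
| 40% | 0.367 | 0.623 |

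**Step 5: are these base rates credible?** The documents give no rate of related non-hematologic grade 3 or higher events for this regimen. Section 1.4.2 reports that 22 of 32 patients (69%) at the same doses had a grade 3 or higher treatment-related event. Neutropenia (31.3%, 10 patients) and febrile neutropenia (12.5%, 4 patients) account for at most 14 of them, so at least 22 − 14 = 8 of 32 (25%) had some other such event. How many of those were non-hematologic is not stated. The 20% to 40% range is therefore an assumption, and so is the 10% dual-fit share.

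**The case against.** The strongest reply is that no sensible investigator reads the 'or' literally. The opening test in 11.3.1 is reasonable possibility, and an event plainly caused by a blocked stent would be scored *Not Related*. That is probably common practice, but the opening test neither ranks the categories nor settles an event that meets two of them.

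The consequences are also cushioned. Suspension is temporary and leads to review by the PI and the safety committee, where misattribution can be found. Section 12.6 reviews grade 4 and 5 events judged unrelated or unlikely. Serious events go to the committee whatever their causality (Section 11.4.1), and adverse events are discussed at weekly cross-site meetings (Section 15.9). This stands and limits the harm. It does not change the count, and the 12.6 review of unrelated events does not extend to grade 3.

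A reader might infer more than the documents support:

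- *That choosing between Related and Possibly Related moves an event across the cut.* It cannot; 12.6 counts both.
- *That nearly every on-treatment event is Related because dosing is every 14 days.* The protocol does not equate occurring during treatment with a temporal relationship.
- *That surgical complications will swell the count.* Surgery is planned 4 to 8 weeks after the last dose, Section 12.5 omits events more than 30 days after the last dose, and Section 11.2 narrows collection after that point. Section 12.6 states no window of its own, but most surgical events are unlikely to enter.
- *That the trial's main safety conclusion turns on this.* The primary endpoint, 30-day post-operative complications, involves no causality judgement.
- *That wording alone could move the counted rate from 30% to 50%, a fourfold rise in suspension probability.* Nothing in the documents supports a shift of that size.

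**Conclusion.** The point holds as a defect in a stated rule. Followed as written, 11.3.1 places an event with a more likely competing cause in categories on both sides of the 12.6 cut and does not say which applies. The suspension count and the causality table are therefore not reproducible between investigators. The main exposure is grade 3 non-hematologic events.

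The size cannot be estimated from the documents. Under the assumed 30% base rate and 10% dual-fit share, the chance of meeting the 5-of-10 limb rises by about 22 percentage points (0.150 to 0.367, a factor of about 2.4) with toxicity unchanged. The calculation assumes independent subjects and ignores the running 50% limb. The wording should be corrected, but the primary analysis is not threatened.

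**What to change.** Rewrite the three upper categories together; changing *Related* alone would leave *Probably Related* demanding dechallenge evidence that the level above it need not have.

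- *Possibly Related*: plausible timing; the drug cannot be excluded, although other causes are also plausible.
- *Probably Related*: plausible timing, consistent with the known drug profile, other causes less likely; dechallenge not mandatory.
- *Related*: all conditions for *Probably Related*, plus either no plausible alternative cause or a positive dechallenge or rechallenge.

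State which category prevails when more than one is met, including at the boundary between *Possibly* and *Probably Not Related*, since that boundary decides the 12.6 count. Replace definite, unrelated and unlikely in Sections 11.2 and 12.6 with the 11.3.1 labels, and say explicitly that 12.6 counts *Possibly Related*, *Probably Related* and *Related*.

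The cost is a wording amendment and a memo to sites. Non-hematologic grade 3 to 5 events already scored will need a causality re-check, and the 12.6 count should then be recalculated.

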### 11.3.2 Intensity of Adverse Events

The intensity of adverse changes in physical signs or symptoms will be graded according to the CTCAE version 4. For all other adverse events not described in the CTCAE, the intensity will be assessed by the Investigator using the following categories:

**Mild** (Grade 1) – transient or mild discomfort; no limitation in activity; no medical intervention/therapy required.

**Moderate** (Grade 2) – mild to moderate limitation in activity, some assistance may be needed; no or minimal medical intervention/therapy required.

**Severe** (Grade 3) – marked limitation in activity, some assistance usually required; medical intervention/therapy required, hospitalization is possible.

**Life-threatening** (Grade 4) – extreme limitation in activity, significant assistance required; significant medical intervention/therapy required, hospitalization or hospice care probable.

**Death** (Grade 5) – the event resulted in death.

### 11.3.3 Action Taken with Study Drug

The action the Investigator took with study drug as a result of the event should be recorded as one of the following:

**None** – No action was taken with regard to the study drug as a result of the adverse event.

**Interrupted** – Study drug was stopped due to the adverse event, but was later resumed at the same dose.

**Dose decreased** – The dose of study drug was decreased as a result of the adverse event.

**Permanently discontinued** – The subject was withdrawn from the study due to the adverse event.

Only one item should be chosen. If multiple actions apply, the following “worst case” scenario hierarchy should be used to determine the preferred entry:

Discontinued > dose decreased > therapy interrupted.

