### 7.3 Dose Modifications

The National Cancer Institute (NCI) Common Toxicity Criteria for Adverse Events Version 4 (CTCAE) will be used to grade toxicity (<http://evs.nci.nih.gov/ftp1/CTCAE/About.html>). All dose reductions for all arms should be based on the worst preceding toxicity. If a subject's dose is reduced during the study due to toxicity, it should remain reduced for the duration of the study; dose re-escalation to an earlier dose is not permitted.

Treatment should be delayed to allow sufficient time for recovery to levels, and upon recovery, treatment should be administered according to the guidelines in the tables below.

If the subject had febrile neutropenia, the ANC must have resolved to  $\geq 1500/\text{mm}^3$  and the subject must have recovered from infection. For Grade 3 or 4 non-hematological toxicities, treatment should be delayed until they resolve to Grade 1 or baseline. Guidelines for dose adjustments of each individual treatment within the regimen are found in the tables below for hematologic toxicities (section 7.3.3), and for non-hematological toxicities (section 7.3.2). In case a patient experiences an infusion reaction, either institutional guidelines or the guidelines provided for infusion reaction management (see Section 6.4) should be followed.

Oxaliplatin may be discontinued if allergic reaction occurs or other toxicity that precludes safe continuation of oxaliplatin, even at lower doses. Subjects may continue to receive irinotecan liposome injection + 5-FU/LV at the discretion of the investigator and continue in the study.

In general, treatment holds may not exceed beyond 14 days without patient removal from this trial unless the situation is discussed and approved by the PI due to circumstances that do not jeopardize the integrity of the trial data or patient safety.

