Grade 4	Hold treatment until AE resolves to $\leq$ Grade 1. 
 
• Reduce the suspected offending agent to Dose Level -1
 
• 2nd occurrence – Discontinue the suspected offending agent
 

* Determination of “clinically significant” Aes and “offending drug” is at the discretion of the treating physician. In all situations where toxicity justifies discontinuation of an agent, only the individual offending agent should be eliminated from the regimen and continuation of treatment otherwise per protocol is recommended.	

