### 7.3.3 Hematologic Toxicity

Toxicity – NCI Grade (v.4)	Suggested Dose Modification
Hematologic Neutrophils/ granulocytes Grade 3,4 or Severe Neutropenia	Hold treatment and check weekly until ANC $\geq$ 1500/mm  . 
 
• 1st Occurrence – Reduce ONIVYDE® to Dose Level -1
 
• 2nd occurrence – Reduce 5-FU infusion to Dose Level -1
 
• 3rd occurrence - Reduce Oxaliplatin to Dose Level -1
 
• 4th occurrence - Reduce ONIVYDE® to Dose Level -2
 
• 5th occurrence - Discontinue ONIVYDE
 
 Either GCSF or Peg-GCSF is permitted when appropriate
Thrombocytopenia Grade 2 (1st Event)	Hold treatment and check weekly until platelets are $\geq$ 75,000/mm  . Resume treatment at same dose level.
Grade 2 (2nd Event) or Grade 3, 4	Hold treatment and check weekly until platelets are $\geq$ 75,000/mm  . 
 
• Upon recovery - Reduce Oxaliplatin to Dose Level -1
 
• 2nd occurrence – Reduce ONIVYDE® to Dose Level -1
 
• 3rd occurrence - Reduce Oxaliplatin to dose level -2
 
• 4th occurrence – Reduce 5-FU to dose level -1
 
• 5th occurrence - Discontinue Oxaliplatin
 
• 6th occurrence - Discontinue ONIVYDE®
 

Other hematologic toxicities do not require dose modification. However, red blood cell transfusion should be considered for hemoglobin < 8 g/dL or significant symptoms of anemia. In all situations where toxicity justifies discontinuation of an agent, only the individual offending agent should be eliminated from the regimen and continuation of treatment otherwise per protocol is recommended after discussion with the PI.

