#### 12.5 Analysis of Safety Data

Safety analyses will be performed on all patients who receive any dose of study medication. Adverse events that occur more than 30 days after the administration of the last dose of treatment will not be included. Safety evaluation will be performed based on the actual therapy received. The safety and tolerability of study drug is determined by reported Aes, physical examinations, laboratory tests, and ECGs. All patients will be assessed regularly for potential occurrence of Aes from the time that treatment starts until 30 days after the last dose of study therapy or 30 days post-operatively, whichever is longer. Aes will be summarized with the incidence and percentage of patients with at least one occurrence of a preferred term (according to the most severe NCI-CTCAE Version 4.0 grade) will be included. The number of Aes reported will also be summarized. Causality (relationship to study drug) will be summarized separately. Duration of AE will be determined and included in listings along with action taken and outcome. Laboratory results will be classified according to NCI-CTCAE, Version 4.0. Incidence of laboratory abnormalities will be summarized; laboratory results not corresponding to an NCI-CTCAE Version 4.0 term will not be graded. Laboratory toxicity shifts from baseline to worst grade will also be provided. The results from physical examination and vital sign measurement will be tabulated. Descriptive statistics will be provided as appropriate.

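### The adverse-event action code for permanent discontinuation is defined as study withdrawal, so an event that permanently ends nal-IRI in a subject who stays on study has no correct code

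*Combined protocol and SAP*

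**What the plan says.** Section 11.3.3 asks the investigator to record the action taken with study drug as None, Interrupted, Dose decreased or Permanently discontinued. Interrupted is defined as "Study drug was stopped due to the adverse event, but was later resumed at the same dose". Permanently discontinued is defined as "The subject was withdrawn from the study due to the adverse event". The section adds "Only one item should be chosen" and, where several actions apply, ranks them "Discontinued > dose decreased > therapy interrupted".

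The treatment sections separate loss of an agent from loss of the subject. Section 7.3 allows oxaliplatin to be stopped and says "Subjects may continue to receive irinotecan liposome injection + 5-FU/LV at the discretion of the investigator and continue in the study". The note to the table in 7.3.2 says that, where toxicity justifies stopping an agent, "only the individual offending agent should be eliminated from the regimen and continuation of treatment otherwise per protocol is recommended". Section 7.3.3 repeats the principle for hematologic toxicity: "continuation of treatment otherwise per protocol is recommended after discussion with the PI".

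Section 12.5 states how the field is used: "Duration of AE will be determined and included in listings along with action taken and outcome".

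**The concern.** The field is headed as an action on a drug, but its most severe category describes subject disposition. In a four-drug regimen whose toxicity rules remove agents one at a time, the two can differ.

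The distinction matters for this trial. The synopsis rationale and section 1.1 say that irinotecan is often reduced or dropped for toxicity, and sections 1.2 and 1.5 offer nal-IRI as a way to improve tolerability and compliance. The primary objective is safety and feasibility. Someone reading the listings will want to see which adverse events cost subjects their nal-IRI, and the code as defined cannot state that for a subject who remained on study.

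**Working it through.** No arithmetic applies and the plan states no figure to reproduce. The check sets the code definitions against the treatment rules.

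**Step 1. Is a single-agent stop with the subject continuing foreseen in current text?** Yes. Section 7.3 says so for oxaliplatin, and the general rules in 7.3.2 and 7.3.3 say so for any offending agent. The ladders show where it can occur:

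- Diarrhea (7.3.2): nal-IRI is stopped at the 5th occurrence.
- Hepatic, grade 3 (7.3.2): nal-IRI is stopped at the 4th occurrence.
- Other clinically significant non-hematologic toxicity (7.3.2): the suspected agent is stopped at the 3rd occurrence for grade 3 and the 2nd for grade 4.
- Neutropenia (7.3.3): nal-IRI is stopped at the 5th occurrence.
- Thrombocytopenia (7.3.3): oxaliplatin is stopped at the 5th occurrence and nal-IRI at the 6th.

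**Step 2. Which code fits an event that permanently ends nal-IRI while the other agents continue?**

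- None: false, because the drug was stopped.
- Interrupted: false, because its definition requires the drug to be resumed at the same dose.
- Dose decreased: misstates a permanent stop and would place it among ordinary dose reductions.
- Permanently discontinued: false by its definition, because the subject was not withdrawn.

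The worst-case ranking does not resolve this. It steers the site to the discontinued category, whose definition asserts a withdrawal that did not happen.

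**Step 3. Does the result depend on what *study drug* means?** Section 10.1 names only liposomal irinotecan under that heading, and section 10.1.8 lists 5-FU, leucovorin and oxaliplatin as other anticancer therapies. Section 3.1 uses the term for the whole regimen in Table 3.1.

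- nal-IRI stop: no code fits under either reading.
- Oxaliplatin stop, term means the regimen: no code fits, for the same reasons.
- Oxaliplatin stop, term means nal-IRI alone: the stop is outside this field, so it is not captured here at all.

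**Step 4. Where does the entry go?** Into the adverse-event listings under section 12.5. Section 12.2 builds the primary endpoint from post-operative events within 30 days of surgery. Section 12.3 takes treatment completion from administration of all eight cycles. Section 12.6 triggers suspension on grade and relatedness. None of these uses the action code.

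**The case against.** The strongest reply is that sites will code by the label. Under a heading about action taken with study drug, a coordinator would probably enter a permanent nal-IRI stop as discontinued. The event would then be visible, and the harm is that two different outcomes share a code. That mixture can be separated in part: section 8.2 requires the reason for study withdrawal on the CRF, so a subject coded as discontinued with no withdrawal record can be identified. For serious events, section 11.4.1 asks follow-up reports to say whether the participant continued or withdrew. These points stand and make the problem smaller. They do not make the definition correct, and they leave the listing dependent on cross-checking.

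Frequency is also a fair objection. Several of the ladders reach nal-IRI discontinuation only at the 5th or 6th occurrence, within eight planned treatments. Shorter routes exist (other grade 3 or 4 toxicity, oxaliplatin allergy), but counting ladder endings does not give a number of cases.

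A reader might infer that every toxicity-driven loss of an agent is miscoded, or that these events are hidden. The documents do not support that: it depends on whether sites follow the definition or the label and, for oxaliplatin, on the meaning of *study drug*. A reader might also infer that dosing records cannot link a stop to the event that caused it. The CRF is not among the documents, so what those forms capture is unknown. They may already record action by agent, but nothing in the protocol says so.

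**Conclusion.** The inconsistency is real and in current text. As defined, section 11.3.3 has no correct code for an adverse event that permanently ends nal-IRI in a subject who stays on study, although 7.3.2 and 7.3.3 provide for that situation. Oxaliplatin stops either share the problem or go unrecorded in the field.

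The consequence is minor. It is confined to the action-taken field and the adverse-event listings. It would be wrong to read it as a threat to the primary endpoint, the sample size, the error rates or the suspension rule. Nor does any stated endpoint measure events leading to loss of nal-IRI; the link to the trial's aims runs through the rationale and the safety and feasibility objective. The number of affected events cannot be derived from the documents.

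The conclusion rests on the protocol text alone and assumes that the unseen CRF follows section 11.3.3.

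**What to change.** Reconcile section 11.3.3 with 7.3, 7.3.2 and 7.3.3:

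- Define *Permanently discontinued* as permanent stopping of the named agent because of the adverse event.
- Record which agent the action applies to. This also removes the dependence on how *study drug* is read.
- Keep withdrawal from the study as a separate item; section 8.2 already requires its reason on the CRF.

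A count by agent of adverse events leading to discontinuation could be added to section 12.5. It would be useful given the rationale, but the inconsistency can be removed without it.

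The cost is a short wording amendment and a small CRF change, with possible re-coding of events already entered. If the CRF already records action by agent, only the protocol wording needs to change. This concerns data coding only and takes no position on when any agent should be stopped.
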